9.2 Baseline

The baseline is defined as the most recent non-missing measurement (scheduled or unscheduled) collected before the first dose of study drug in each cohort.

10 INTERIM ANALYSES AND DATA SAFETY MONITORING

There is no interim analysis plan for this study.

11 GENERAL INFORMATION RELATED TO DATA PRESENTATIONS

The formats and layouts of TFLs are provided in a separate document and are common displays. Their numbering and general content follow the International Conference on Harmonisation (ICH) E3 guidelines. Actual formats and layouts may be altered slightly from those presented as necessary to accommodate actual data or statistics.

Minor format changes will not require updates to the SAP; rather they may be documented in a Note to SAP.

APPENDIX A STUDY SCHEDULE(S)

Study Procedures	Screening (28 days prior to randomization)	In-patient admission	Treatment Period		Clinic Discharge	Follow-up Period		Early Termination (ET)
Study Day	Days -28 to -1	Day -1	Day 1	Days 2 to 14	Day 15	Day 23 ±1 day Clinic Visit	Day 42 ±2 days Telephone call	
Informed Consent	X							
Admission ¹		X						
Clinic Confinement			X	X				
Discharge					X			
Medical and Surgical History	X							
Physical Examination	X				X	X		X
Demographic information	X							
Body Height/Body Weight	X							
Vital Signs ²	X	X	X	X	X	X		X
12-lead ECG ³	X		X	X	X	X		X

¹ Subjects will be admitted to the clinical research unit at least 16 hours prior to the first study drug administration.

² Vital signs will include blood pressure, heart rate and oral body temperature. On Days 1 to 14, vital signs will be measured within 1 hour prior to dosing using the same arm, if possible, after 5 minutes in seated position.

Study Procedures	Screening (28 days prior to randomization)	In-patient admission	Treatment Period		Clinic Discharge	Follow-up Period		Early Termination (ET)
Study Day	Days -28 to -1	Day -1	Day 1	Days 2 to 14	Day 15	Day 23 ±1 day Clinic Visit	Day 42 ±2 days Telephone call	
Safety Laboratory Tests ⁴	X	X		X	X	X		X
Serology (HIV/HBV/HCV)	X							
Serum Pregnancy Test (females of childbearing potential only)	X							
Urine Pregnancy Test (females of childbearing potential only)		X						
COVID-19 Test ⁵	X	X						
Urine Drug Screen and Alcohol Breath or Urine Test	X	X						
Inclusion/Exclusion Criteria	X	X						
Randomization			X					
Fasted Study Drug			X	X				

³ On Day 1, ECGs will be conducted pre-dose and 1 hour (±10 minutes) after the third dose of Day 1. On Days 7, 13, and 14, ECGs will be performed prior to first daily dose.

⁴ Safety laboratory tests (chemistry, hematology, and urinalysis) will be performed on Day -1, Day 7 (pre-dose), Day 15, and Day 23. For all subjects, total cholesterol, high-density lipoprotein, low-density lipoprotein, and triglycerides will not be included in the safety laboratory tests performed on Day -1. For subjects who are screened within 5 days of check-in (on Day -6 to Day -2), the safety laboratory tests will not be performed on Day -1.

⁵ The COVID-19 test should be repeated upon check-in on Day -1 using a COVID rapid antigen test kit or PCR. Additionally, study site and local health authority policies and recommendations can be applied for compliance. If the initial result is positive at the Screening Visit, the test may be repeated after 14 days or on Day -1 whichever comes first.

Study Procedures	Screening (28 days prior to randomization)	In-patient admission	Treatment Period		Clinic Discharge	Follow-up Period		Early Termination (ET)
Study Day	Days -28 to -1	Day -1	Day 1	Days 2 to 14	Day 15	Day 23 ±1 day Clinic Visit	Day 42 ±2 days Telephone call	
Administration (all doses)								
Baseline and Trough plasma lithium and peak plasma salicylate concentration measurements ⁶			X	X				X
MMSE Score (AD subjects only)	X							
Hachinski Ischemic Scale Score ⁷ (AD subjects only)	X							
Meals ⁸		X	X	X	X			

⁶ Blood samples for baseline plasma lithium and plasma salicylate concentration measurements will be collected before first dose on Day 1. Blood samples for trough plasma lithium and peak plasma salicylate concentration measurements will be collected on Days 3, 5, 7, 10, 13, and 14, and at the discretion of the Investigator (the latter are 'Safety Samples' for Therapeutic Drug Monitoring), particularly to assess the relationship to possible lithium or salicylate related AEs. These safety samples could be sent for expedited analysis to either a local laboratory with an aliquot saved for the bioanalytical laboratory, or to the bioanalytical laboratory directly (Sannova or Altasciences). In addition, for AD subject Cohorts 2b, 3b, 4b, and 5b, the trough lithium sample on Day 5 will be treated as a 'Safety Sample' for Therapeutic Drug Monitoring to assess any lithium-related PK exposure safety concerns at an early treatment time point which may require dosing to be discontinued for an individual subject. This sample will be sent to Sannova for expedited analysis. Similarity between Days 13 and 14 trough lithium plasma levels and peak salicylate plasma levels will be used to determine the status of lithium and salicylate steady-state PK conditions, and/or by another appropriate method, such as linear regression. Blood collection for trough lithium plasma concentrations will occur just prior to the first daily dose, while blood collection for peak plasma salicylate concentrations will occur at 1.25 hours post third daily dose (the estimated time to a maximum blood concentration C_{max}). For early termination, blood samples for lithium and salicylate plasma concentrations will be collected. A ±10-minute window will be allowed for collection of PK samples for both lithium and salicylate.

⁷ Hachinski Ischemic Scale Score is presented in protocol APPENDIX 5.

Study Procedures	Screening (28 days prior to randomization)	In-patient admission	Treatment Period		Clinic Discharge	Follow-up Period		Early Termination (ET)
Study Day	Days -28 to -1	Day -1	Day 1	Days 2 to 14	Day 15	Day 23 ±1 day Clinic Visit	Day 42 ±2 days Telephone call	
Adverse Event Reporting/Safety-Tolerability Assessment	X	X	X	X	X	X	X	X
Prior Medications	X	X						
Concomitant Medications	X	X	X	X	X	X	X	X
Health Status Questionnaire (SF-36)						X	X	X

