
To explore the difference in pharmacokinetic (PK) profile between the non-elderly vs elderly subjects (healthy subjects only).For AD subject cohorts (Cohorts 1, 2b, 3b, 4b, and 5b), determination of qualitative and quantitative evaluations of AD subject desirable characteristics for future Phase 2 and 3 clinical studies in order to:
facilitate recruitment into subsequent AL001 clinical trials.facilitate trial-adherence to completion of study requirements including treatment adherence.		
Study Design and Conduct:		
This was a Phase 1/2a, multi-center, double-blind, placebo-controlled, randomized, multiple ascending dose (MAD) clinical study to determine the safety and maximum tolerated dose (MTD) of AL001 in subjects with mild-to-moderate AD (Food and Drug Administration Classification of Stage 2 to 4 AD) and healthy adult subjects. Cohorts 1, 2b, 3b, 4b, and 5b were planned to include AD subjects (between the ages of 50 and 80 years, inclusive) and Cohorts 2a, 3a, 4a, and 5a were planned to include healthy subjects (non-elderly adults between the ages of 18 to 64 years, inclusive, and healthy elderly adults between the ages of 65 to 80 years, inclusive).		
Each cohort was enrolled sequentially and randomized separately using a standard computerized method. The data from the previous cohort was deemed safe before the next sequential cohort was enrolled and dosing initiated.		
Cohort 1 was planned to include 8 AD subjects (6 active and 2 placebo). Each of the Cohorts 2 to 5 was sub-divided into 2 cohorts: Cohorts 2a, 3a, 4a, and 5a (healthy subjects) and Cohorts 2b, 3b, 4b, and 5b (AD subjects).		
At each dose level in Cohorts 2 to 5, the healthy subject cohort "a" (up to 8 subjects) was first completed up to Day 15 and the blinded safety (laboratory reports, AEs, tolerability) and PK data collected up to that point were reviewed by the Safety Review Committee. The initiation of the next dose cohort could be delayed up to approximately 4 weeks following the last dose of the last subject in the preceding cohort to allow for this process. If the dose level was endorsed as safe, the committee permitted progression to the AD subject cohort "b" at the same dose level, as well as progression to the next dose level of healthy subject cohort. The healthy subject cohorts proceeded to the next higher dose level		

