Name of Sponsor/Company: Alzamend Neuro, Inc.	Individual Study Table Referring to Part of the Dossier	(For National Authority Use Only)
Name of Finished Product: AL001	Volume:	
Name of Active Ingredient: Lithium salicylate/L-proline cocrystal	Page:	

without having to wait for the corresponding AD subject cohort to be completed and reviewed by the Safety Review Committee.

Cohort 5b was planned but was not conducted due to PK-based stopping rules designed to assure that the assigned MTD is unlikely to result in plasma trough lithium concentrations above 1.0 mEq/L (healthy elderly and Alzheimer's subjects) and 1.2 mEq/L (healthy non-elderly subjects). For salicylate, the maximum threshold value was 30 mg/dL for all subjects. These values pertain to subjects/patients with adequate renal function (estimated glomerular filtration rate [eGFR] \geq 60 mL/minute/1.73 m²).

For each cohort in which the subjects were dosed, subjects were randomized to 1 of 2 treatment groups in a 6:2 ratio of AL001 (active study medication) to placebo. Subjects in each of these cohorts were dosed 3 times daily (TID) for 14 days at the planned dose level indicated in the table below or placebo:

Cohort	Lithium Carbonate Equivalent Daily Dosing Level	No. of AL001 210 mg Capsules	AL001 Daily Dose
Cohort 1	60% of 450 mg lithium carbonate	3 capsules TID	1890 mg \times 14 days
Cohort 2a/ Cohort 2b	100% of 450 mg lithium carbonate	5 capsules TID	3150 mg \times 14 days
Cohort 3a/ Cohort 3b	140% of 450 mg lithium carbonate	7 capsules TID	4410 mg \times 14 days
Cohort 4a/ Cohort 4b	160% of 450 mg lithium carbonate	8 capsules TID	5040 mg \times 14 days
Cohort 5a/ Cohort 5b	200% of 450 mg lithium carbonate	10 capsules TID	6300 mg \times 14 days ^a

Abbreviation: TID = 3 times daily.

Note: 7 mg of AL001 has the lithium content of 1 mg lithium carbonate

a. Lithium dose equivalent to that routinely used for bipolar disorder type 1 treatment.

Subject population:

Cohorts 1, 2b, 3b, 4b, and 5b:

Male and female adult subjects with mild-to-moderate AD, between the ages of 50 and 80 years, inclusive

Cohorts 2a, 3a, 4a, and 5a:

Healthy adult male and female subjects, between the ages of 18 to 64 years, inclusive (non-elderly) and between the ages 65 to 80 years, inclusive (elderly).

Name of Sponsor/Company: Alzamend Neuro, Inc.	Individual Study Table Referring to Part of the Dossier	(For National Authority Use Only)
Name of Finished Product: AL001	Volume:	

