7.3 Statistical Analysis

In order to assess whether PK steady state has been approximately achieved, descriptive statistics for trough (Cmin) measurements of plasma lithium and Cmax (peak) measurements of plasma salicylate will be presented for all available days by cohort and overall. In addition, these measurements for plasma lithium and salicylate on Days 13 and 14 for each cohort will be \log^e -transformed and a 90% CI for the difference in the measurements between Days 13 and 14 for lithium and salicylate will be calculated on the \log^e scale and then transformed back to the original scale for each cohort. If the 90% CI on the original scale is contained within the interval 85.0% to 117.6%, then an approximation of steady state will be concluded for the respective analyte and cohort. Alternative approaches to estimate achievement of steady-state conditions are to be used, as appropriate, such as when at least 3 trough concentrations for plasma lithium and/or at least 3 Cmax concentrations for plasma salicylate can be assessed using linear regression. All cohorts except Cohort 1 are expected to complete at least 3 lithium trough and 3 salicylate peak concentration measurements and should be candidates for this statistical approach.

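### The expedited Day 5 lithium trough covers only AD Cohorts 2b to 5b; healthy Cohorts 2a to 5a, dosed first and half elderly on AL001, have the same draw but no scheduled result during dosing

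*SAP*

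**What the plan says.** Footnote 6 to the SAP's Appendix A sets lithium trough draws on Days 3, 5, 7, 10, 13 and 14, just before the first daily dose, and does not restrict them to particular cohorts. SAP section 7.3 fits this: "All cohorts except Cohort 1 are expected to complete at least 3 lithium trough and 3 salicylate peak concentration measurements".

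The footnote describes two kinds of Safety Sample:

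- **Discretionary, any cohort.** The investigator may take extra samples, mainly to relate adverse events to exposure. "These safety samples could be sent for expedited analysis to either a local laboratory" or to the bioanalytical laboratory. Expedited assay is allowed, not required.
- **Scheduled, AD cohorts only.** The footnote adds that "for AD subject Cohorts 2b, 3b, 4b, and 5b, the trough lithium sample on Day 5 will be treated as a" Safety Sample, to pick up lithium exposure concerns "at an early treatment time point which may require dosing to be discontinued for an individual subject". On handling, the footnote is definite: "This sample will be sent to Sannova for expedited analysis".

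On the order of dosing, the protocol synopsis says that at each level from 2 to 5 the healthy cohort "was first completed up to Day 15 and the blinded safety (laboratory reports, AEs, tolerability) and PK data collected up to that point were reviewed". Only after this committee review could the AD cohort start. SAP section 3.4 stratifies each healthy cohort by age, with 3 elderly and 3 non-elderly subjects on AL001 and one of each on placebo. The synopsis describes stopping rules meant to keep the MTD from producing "plasma trough lithium concentrations above 1.0 mEq/L (healthy elderly and Alzheimer's subjects) and 1.2 mEq/L (healthy non-elderly subjects").

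**The concern.** The plan gives its own reason for the Day 5 check: to find a high lithium exposure early enough to stop that person's dosing. The check is scheduled only in the group dosed second at each of the four shared levels. The group dosed first includes elderly subjects, for whom the plan uses the same 1.0 mEq/L figure as for AD subjects.

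Committee review does not fill this gap. It follows completion to Day 15, when all dosing is over, so it protects the next cohort and not the subject now being dosed. Discretionary samples are aimed chiefly at possible adverse events, so a high trough without symptoms could go unread until dosing has ended. What is at stake is the chance to act on such a trough in an individual healthy subject, above all an elderly one.

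**Working it through.** **Planned numbers.** SAP section 3.5 gives a maximum of 72 subjects: 5 × 8 AD + 4 × 8 healthy = 40 + 32 = 72, which reproduces. At the four shared dose levels:

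- AD Cohorts 2b to 5b on AL001: 4 × 6 = 24, all with the scheduled expedited check.
- Healthy Cohorts 2a to 5a on AL001: 4 × 6 = 24, none with it. Elderly: 4 × 3 = 12.

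AD Cohort 1, the lowest dose, also lacks the check.

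**Doses still to come at the Day 5 draw.** Dosing is three times daily for 14 days (SAP section 3.2): 14 × 3 = 42 doses. The trough precedes the first dose of Day 5, so 4 × 3 = 12 doses have been given and 42 − 12 = 30 remain (30/42 = 71%). The documents state no turnaround time. Assuming that the result is available before the first dose of the day:

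| Assumed turnaround | Doses remaining | Share of 42 |
|---|---|---|
| 1 day | 30 − 3 = 27 | 64% |
| 2 days | 30 − 6 = 24 | 57% |
| 3 days | 30 − 9 = 21 | 50% |

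Across this range at least half of the course could still be changed.

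**Dose context.** The synopsis equates 7 mg of AL001 with 1 mg of lithium carbonate. Cohorts 2a, 3a, 4a and 5a therefore receive 3150/7 = 450, 4410/7 = 630, 5040/7 = 720 and 6300/7 = 900 mg/day. The last is described as "Lithium dose equivalent to that routinely used for bipolar disorder type 1 treatment". As shares of 900 mg these are 50%, 70%, 80% and 100%.

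**What healthy subjects have during dosing.**

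| Safeguard | Source | Scheduled lithium result during dosing? |
|---|---|---|
| Routine troughs, six days | Appendix A, footnote 6 | Drawn; assay timing not stated |
| Discretionary Safety Samples | Appendix A, footnote 6 | Only if the investigator asks |
| Day 7 laboratory tests, with creatinine and electrolytes | Appendix A, footnote 4; Table 6 | No; lithium is not in Table 6 |
| Daily vital signs; ECGs on Days 1, 7, 13 and 14 | Appendix A, footnotes 2 and 3 | No |
| Committee review | Synopsis | After Day 15 |

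**Assays needed.** Elderly only, placebo included to keep the blind: 4 × (3 + 1) = 16. All healthy subjects: 4 × 8 = 32. The plan already expedites 4 × 8 = 32 in Cohorts 2b to 5b.

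**The case against.** The strongest objection is that the file is incomplete. The SAP rests on protocol version 8.0 (SAP section 1), while the protocol document available is a report synopsis. Rules for stopping an individual, sample handling and assay timing belong in the full protocol. If healthy-cohort samples were in fact assayed promptly, there would be no gap. This stands, and it limits the point to what the available documents show.

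Treating AD subjects more cautiously is also defensible. They have comorbidities and concomitant medications, and may report symptoms less reliably. That explains a check in AD subjects. It does not explain leaving it out for elderly healthy subjects who receive the dose earlier.

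Other safeguards lower the risk. The thresholds apply to subjects with eGFR of at least 60 mL/minute/1.73 m². Subjects are confined and have the monitoring tabulated above. Doses rise in steps, and none exceeds a level described as routine in bipolar disorder. All of this bears on severity, but none of it gives a lithium reading.

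A reader might infer three stronger things that the documents do not support:

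- *Healthy cohorts have no lithium sampling.* They have six scheduled troughs. The difference is the expedited handling of one of them.
- *A trough above 1.0 mEq/L should have stopped a healthy elderly subject.* The figure is an MTD endpoint and stopping-rule value, not a stated limit for individual discontinuation.
- *Healthy subjects were harmed.* Nothing shows this, and the synopsis reports no undue safety concerns.

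**Conclusion.** The point holds as a gap in scheduled monitoring. In the available documents, 24 planned AL001 subjects in Cohorts 2a to 5a, 12 of them elderly, have a Day 5 trough drawn but no scheduled lithium result during dosing, although they receive each dose first. The AD subjects who follow at the same dose have one. An expedited result would come while 50% to 71% of doses remain, the lower end resting on an assumed turnaround of up to 3 days.

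The conclusion assumes that protocol version 8.0 adds no rule for healthy cohorts and that routine samples are not assayed quickly enough to serve the same purpose. Neither could be checked. It is best classed as a cheap improvement: the sample exists, and the plan's own reasoning supports reading it early.

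**What to change.** Amend footnote 6 and the matching protocol schedule so that the Day 5 lithium trough already drawn in Cohorts 2a to 5a, at minimum in all elderly subjects, is also a Safety Sample sent for expedited analysis. Use 1.0 mEq/L (elderly) and 1.2 mEq/L (non-elderly) as flags for review, not as automatic stops. Send these results to the Medical Monitor or another recipient outside the blinded site team. If protocol version 8.0 already provides for this, a cross-reference in footnote 6 is enough.

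The cost is 16 expedited assays for elderly subjects only, or 32 for all healthy subjects, with no new visit or blood draw. There are two downsides. One is the assay fees. The other is that a measurable lithium value may reveal allocation to whoever receives it; with 3 active and 1 placebo in each age stratum, one lithium-free result would identify that stratum's placebo subject. SAP section 3.4 already lets the Medical Monitor unblind a subject when a safety issue requires it, so that role is a natural recipient.

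Because the change affects conduct, amending the SAP alone would not be enough. The synopsis gives a completion date of 2023/05/15, so in practice the change would apply to later multiple-dose studies of AL001.

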1 INTRODUCTION

This statistical analysis plan (SAP) provides a detailed description of the statistical methods and procedures to be implemented for the analyses of data from protocol AL001-ALZ02. The analyses described in the SAP are based upon the final protocol version 8.0 (Amendment 06) dated 2022/11/28.

2 STUDY OBJECTIVES

The objectives of the study and corresponding study endpoints are detailed in Table 1.

Table 1: Objectives and Related Endpoints

Objective	Endpoint	Analysis
Primary		
To evaluate the safety and tolerability of AL001 under multiple-dose, steady-state conditions in Alzheimer's subjects and healthy adult subjects.	
 • Vital signs (blood pressure, heart rate, and oral body temperature) • 12-lead electrocardiogram • Physical examination • Safety laboratory tests (hematology, chemistry [including thyroid-stimulating hormone (TSH), vitamin B12, and Mg], HbA1c, and urinalysis • Reported and observed Adverse events (AEs)/serious AEs)/tolerability observations including signs and/or symptoms of lithium and/or salicylate toxicity 	Refer to Section 8
Secondary		
To characterize the Maximum tolerated dose (MTD) of AL001 in patients with mild to moderate Alzheimer's disease (AD) and healthy adult subjects.	
 • Prevalence of peak salicylate concentrations above 30 mg/dL • Prevalence of trough plasma lithium concentrations above 1.2 mEq/L for healthy adult subjects or 1.0 mEq/L for healthy elderly and Alzheimer's subjects. 	Refer to Section 7
Exploratory		
To explore the difference in PK profile between the non-elderly vs elderly subjects (healthy subjects only).	
 • Descriptive statistics for PK will be presented by treatment group and compared between non-elderly and elderly subjects. 	Refer to Section 7
For AD subject cohorts (Cohorts 1, 2b, 3b, 4b, and 5b), determination of qualitative and quantitative evaluations of AD subject desirable characteristics for future Phase 2 and 3 clinical studies in order to: 
 • facilitate recruitment into subsequent AL001 clinical trials • facilitate trial-adherence to completion of study requirements including treatment adherence 	
 • Demographic characteristics of all screened and successfully enrolled AD subjects will be documented to determine what AD subject characteristics are needed and appropriate for successful recruitment and adherence to treatment and study requirements in future Phase 2 and 3 clinical studies. Baseline Mini-Mental State Examination scores, FDA classifications (protocol APPENDIX 3) and demographic characteristics, for example, will be reviewed for relationship to AD subjects' ability to provide informed consent and complete study requirements. 	Refer to Section 6

3 STUDY DESIGN

3.1 General Description

This is a Phase 1/2a, multi-center, double-blind, placebo-controlled, randomized, MAD clinical study to determine the safety and MTD of AL001 in subjects with mild to moderate AD (FDA Classification of Stage 2 to 4 AD [protocol APPENDIX 3]) and healthy adult subjects. Cohorts 1, 2b, 3b, 4b, and 5b will include AD subjects (between the ages of 50 and 80 years, inclusive) and Cohorts 2a, 3a, 4a, and 5a will include healthy subjects (non-elderly adults between the ages of 18 to 64 years, inclusive, and healthy elderly adults between the ages of 65 to 80 years, inclusive). In each of the 9 cohorts, subjects will be confined to the study site from Day -1 until Day 15.

The study consists of 3 phases.

1. Screening Phase – up to 28 days (from Days -28 to -1)
2. Treatment Phase – 16 days:
 - Subjects will be admitted to the study site on Day -1. Subjects will receive 14 days of 3 times daily (TID) dosing with assigned study medication from Days 1 to 14 and will remain confined until Day 15.
 - Each of the 9 cohorts will be initiated sequentially starting with Cohort 1 and progressing through to Cohort 5 depending on acceptable review of the safety data by a 3-member expert adjudication panel. Each of the Cohorts 2 to 5 will be subdivided into 2 cohorts: Cohorts 2a, 3a, 4a, and 5a will include healthy subjects and Cohorts 2b, 3b, 4b, and 5b will include AD subjects. The results from the healthy subject cohorts ‘a’ will be reviewed by the independent safety adjudication committee and if assessed as safe, the committee will permit progression to the corresponding AD subject cohort ‘b’ at the same dose level, as well as progression to the next dose level of healthy subject cohort. The healthy subject cohorts can proceed to the next higher dose level without having to wait for the corresponding AD subject cohort to be completed and reviewed by the safety adjudication panel.
 - The initiation of the next dose cohort may be delayed up to approximately 4 weeks following the last dose of the last subject in the preceding cohort. This is necessary to allow time for the safety and PK data to be compiled and tabulated for review by the safety committee (laboratory reports, AEs, tolerability, and PK data from all [up to 8] completed subjects in each cohort), to determine if it is safe to proceed with enrollment of the subsequent cohort.
3. Follow-up Phase - 1 month
 - Subjects will be followed-up after discharge from the study site on Day 15, with a post-treatment clinic visit on Day 23 and a post-treatment telephone call on Day 42.

Each patient will participate in the study for up to approximately 2.5 months.

